**Table 6 Dose Modification Criteria for AL101**

Dose Modification Criteria for AL101 -Related Adverse Events	AL101 modification	
	Note: for any questions, please contact the Sponsor's Medical Monitor.	
	Cohort 1 (4 mg QW IV)	Cohort 2 (6 mg QW IV)
Grade 4 neutropenia lasting $\geq$ 7 days	Decrease by 1 dose level to 2.4 mg QW.	Decrease dose to 4 mg QW for first episode and to 2.4 mg QW for second episode
Grade 3 febrile neutropenia lasting $>$ 24 hours	Decrease by 1 dose level to 2.4 mg QW.	Decrease dose to 4 mg f QW or first episode and to 2.4 mg QW for second episode.
Grade 4 febrile neutropenia	Discontinue.	Discontinue.
Grade 4 thrombocytopenia or $\geq$ Grade 3 thrombocytopenia with significant bleeding	Decrease by 1 dose level to 2.4 mg QW.	Decrease dose to 4 mg QW for first episode and to 2.4 mg QW for second episode
$\geq$ Grade 3 CD4+ T-cell depletion (counts $<$ 200 cells/ $\mu$ L)	Interrupt AL101 until resolution to Grade 1, then resume at 1 dose level lower (i.e., 2.4 mg QW) . If treatment interruption is longer than 28 days, the patient will be discontinued from the study.	Interrupt AL101 until resolution to Grade 1, then resume at 4 mg QW dose level. For second episode, reduce dose to 2.4 mg QW.  If treatment interruption is longer than 28 days, the patient will be discontinued from the study.
Grade 1 diarrhea	No change in AL101 dose. Guidelines for the management of diarrhea: 
 
• Loperamide 4 mg at the first onset of diarrhea, then 2 mg every 2 hours around-the-clock until diarrhea free for at least 12 hours. Patients may take loperamide 4 mg every 4 hours during the night. These doses should not be used for more than 48 hours due to the risk of paralytic ileus.
 
• For patients that cannot tolerate loperamide or do not get adequate relief with maximum
 
	No change in AL101 dose. Guidelines for the management of diarrhea: 
 
• Loperamide 4 mg at the first onset of diarrhea, then 2 mg every 2 hours around-the-clock until diarrhea free for at least 12 hours. Patients may take loperamide 4 mg every 4 hours during the night. These doses should not be used for more than 48 hours due to the risk of paralytic ileus.
 
• For patients that cannot tolerate loperamide or do not get adequate relief with maximum doses, standard doses of LOMOTIL®
 

Confidential

 Document State: Effective (Controlled)  
 CONFIDENTIAL

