	
improvement within 3 days with maximum doses of loperamide:
 
 
• Patient may be treated with dexamethasone at a dose of 8 mg every 8 hours (Q8h) for up to 5 days. If still no improvement in symptoms, the patient may continue with the dexamethasone or consider switching to budesonide 9 mg once daily (QD). Refer to Section 7.1.2 for additional instructions on premedication with steroids.
 
 
Dose modifications for AL101:
 
Interrupt AL101 until resolution to <math>\leq</math> Grade 1 (refer to Section 7.1.2 for management guidelines for diarrhea and above for management guidelines for diarrhea).
 
Decrease AL101 dose to 2.4 mg QW.
 
If the diarrhea does not resolve to Grade 1 by 14 days, the patient will be discontinued from AL101 (refer to Section 4.5 for early withdrawal of patients from therapy or assessment).
 
If treatment interruption is longer than 28 days, the patient will be discontinued from AL101 (refer to Section 4.5 for early withdrawal of patients from therapy or assessment).
	
improvement within 3 days with maximum doses of loperamide:
 
 
• Patient may be treated with dexamethasone at a dose of 8 mg Q8h for up to 5 days. If still no improvement in symptoms, the patient may continue with the dexamethasone or consider switching to budesonide 9 mg QD. Refer to Section 7.1.2 for additional instructions on premedication with steroids.
 
 
Dose modifications for AL101:
 
Interrupt AL101 until resolution to <math>\leq</math> Grade 1 (refer to Section 7.1.2 and above for management guidelines for diarrhea).
 
Change dose regimen to 6 mg 2 weeks on / 1 week off for first episode
 
Decrease AL101 dose to 4 mg QW for second episode and to 2.4 mg QW for third episode.
 
If the diarrhea does not resolve to Grade 1 by 14 days, the patient will be discontinued from AL101 (refer to Section 4.5 for early withdrawal of patients from therapy or assessment).
 
If treatment interruption is longer than 28 days, the patient will be discontinued from AL101 (refer to Section 4.5 for early withdrawal of patients from therapy or assessment).

Grade 3 diarrhea	Guidelines for the management of diarrhea:	Guidelines for the management of diarrhea:

Confidential

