Confidential

 Document State: Effective (Controlled)  
 CONFIDENTIAL

Page 56 of 118

Dose Modification Criteria for AL101 -Related Adverse Events	AL101 modification	
	Note: for any questions, please contact the Sponsor's Medical Monitor.	
	Cohort 1 (4 mg QW IV)	Cohort 2 (6 mg QW IV)
	
Interrupt AL101 until resolution to <math>\leq</math> Grade 1 (refer to Section 6.6.2 and above for management guidelines for diarrhea).
 
Decrease AL101 dose to 2.4 mg QW.
 
If the diarrhea does not resolve to Grade 1 by 14 days, the patient will be discontinued from AL101 (refer to Section 4.5 for early withdrawal of patients from therapy or assessment).
 
If treatment interruption is longer than 28 days, the patient will be discontinued from AL101 (refer to Section 4.5 for early withdrawal of patients from therapy or assessment).
	
Interrupt AL101 until resolution to <math>\leq</math> Grade 1 (refer to Section 7.1.2 and above for management guidelines for diarrhea).
 
Change dose regimen to 6 mg 2 weeks on / 1 week off for the first episode.
 
Decrease AL101 dose to 4 mg QW for second episode and to 2.4 mg QW for third episode
 
If the diarrhea does not resolve to Grade 1 by 14 days, the patient will be discontinued from AL101 (refer to Section 4.5 for early withdrawal of patients from therapy or assessment).
 
If treatment interruption is longer than 28 days, the patient will be discontinued from AL101 (refer to Section 4.5 for early withdrawal of patients from therapy or assessment).

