	
 
For patients that cannot tolerate loperamide or do not get adequate relief with maximum doses, standard doses of LOMOTIL® (diphenoxylate/atropine) may be added or used instead of loperamide.
 
Additional antidiarrheal measures, such as octreotide, may be used at the discretion of the investigator or treating physician
 
Treat with dexamethasone at a dose of 8 mg every Q8h for up to 5 days. If still no improvement in symptoms, the patient may continue with the dexamethasone or consider switching to budesonide 9 mg QD. Refer to Section 7.1.2 for additional instructions on premedication with steroids.
 
 
If the above measures have not worked, or patient has progressed to Grade 4, consult GI as necessary to evaluate for colitis.
 
Dose modifications for AL101:
 
Permanently discontinue AL101 (refer to Section 4.5 for early withdrawal of patients from therapy or assessment).
	
standard doses of LOMOTIL® (diphenoxylate/atropine) may be added or used instead of loperamide.
 
 
Additional antidiarrheal measures, such as octreotide, may be used at the discretion of the investigator or treating physician
 
Treat with dexamethasone at a dose of 8 mg Q8h for up to 5 days. If still no improvement in symptoms, the patient may continue with the dexamethasone or consider switching to budesonide 9 mg QD. Refer to Section 7.1.2 for additional instructions on premedication with steroids.
 
 
If the above measures have not worked, or patient has progressed to Grade 4, consult GI as necessary to evaluate for colitis.
 
Dose modifications for AL101:
 
Permanently discontinue AL101 (refer to Section 4.5 for early withdrawal of patients from therapy or assessment).

Diagnosed or suspected clinically significant gastrointestinal (GI) bleeding or unexplained drop in hemoglobin	
Interrupt AL101, perform appropriate diagnosis and treatment.
 
If GI bleeding is considered related to AL101 reduce 1 dose level to 2.4 mg QW.
	
Interrupt AL101, perform appropriate diagnosis and treatment.
 
If GI bleeding is considered related to AL101, Decrease to 4 mg QW for first episode and to 2.4 mg QW for second episode 1 dose level.

Confidential

 Document State: Effective (Controlled)  
 CONFIDENTIAL

Page 58 of 118

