Any other AL101-related Grade 3 nonhematologic adverse event except electrolyte abnormalities that may be managed with supplements	Interrupt AL101 until resolution to $\leq$ Grade 1 and then resume at 1 dose level lower (i.e., 2.4 mg QW). If treatment interruption is longer than 28 days, the patient will be discontinued from the study (refer to Section 4.5 for early withdrawal of patients from therapy or assessment).	Interrupt AL101 until resolution to $\leq$ Grade 1 and then change dose regimen to 6 mg 2 weeks on / 1 week off for the first episode. Decrease dose to 4 mg QW for second episode and to 2.4 mg QW for third episode. If treatment interruption is longer than 28 days, the patient will be discontinued from the study (refer to Section 4.5 for early withdrawal of patients from therapy or assessment).

Confidential

 Document State: Effective (Controlled)  
 CONFIDENTIAL

Page 60 of 118

Dose Modification Criteria for AL101 -Related Adverse Events	AL101 modification	
	Note: for any questions, please contact the Sponsor's Medical Monitor.	
	Cohort 1 (4 mg QW IV)	Cohort 2 (6 mg QW IV)
Grade 4 non-hematologic AEs including Grade 4 non-hematologic lab abnormalities lasting > 72 hours	Permanently discontinue from IP (refer to Section 4.5 for early withdrawal of patients from therapy or assessment ).	Permanently discontinue from IP (refer to Section 4.5 for early withdrawal of patients from therapy or assessment ).

Confidential

 Document State: Effective (Controlled)  
 CONFIDENTIAL

Page 61 of 118

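### Ten Cohort 2 rows of Table 6 fix the dose by an undefined episode number and ignore the current dose; after one earlier two-step episode, three of them name no dose below 4 mg QW

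*Protocol*

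**What the plan says.** Protocol Section 6.6 sends sites to Table 6 for dose modification. It also states a general rule: related Grade 3 non-hematological toxicity (apart from certain isolated, quickly reversed electrolyte abnormalities) and Grade 4 hematological toxicity lead to a reduction of one dose level. Intolerable Grade 2 toxicity is decided case by case with the sponsor. Re-escalation after a reduction needs Medical Monitor approval.

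Ten of the 19 rows of Table 6 give the Cohort 2 step by episode number.

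- **Seven two-step rows** go to 4 mg QW, then 2.4 mg QW: Grade 4 neutropenia, Grade 3 febrile neutropenia, thrombocytopenia, CD4+ T-cell depletion, GI bleeding, AST/ALT and triglycerides. The neutropenia and thrombocytopenia cells read "Decrease dose to 4 mg QW for first episode and to 2.4 mg QW for second episode". The CD4 cell says "then resume at 4 mg QW dose level" and names 2.4 mg QW for a second episode.
- **Three three-step rows** put a schedule change first. Grade 3 diarrhea: "Change dose regimen to 6 mg 2 weeks on / 1 week off for the first episode", then "Decrease AL101 dose to 4 mg QW for second episode and to 2.4 mg QW for third episode". Grade 2 diarrhea starts with "Change dose regimen to 6 mg 2 weeks on / 1 week off for first episode" and has the same later steps. Other Grade 3 nonhematologic events: "then change dose regimen to 6 mg 2 weeks on / 1 week off for the first episode", then "Decrease dose to 4 mg QW for second episode and to 2.4 mg QW for third episode".

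Table 10 (Section 8.4.2) handles Grade 2 colitis differently. It separates patients on 6 mg QW from those on 4 mg QW and sends the latter to 2.4 mg QW.

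**The concern.** A step-down rule has to say where the patient is stepping down from. These cells do so only for someone still on 6 mg QW. Once a patient has been reduced for one toxicity, the instruction for a different one depends on how episodes are counted, and the protocol does not say whether that is per row or across toxicities. In some cells neither count leads to a lower dose.

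This matters more in Cohort 2 than it would at a lower starting dose. Section 1.3.2 reports that the previous developer recommended 4 mg as the weekly MTD in solid tumors, and Section 1.4.1 reports dose-limiting toxicities at 6 mg and 8.4 mg. Cohort 2 starts above that MTD, so it leans on its reduction rules. Section 6.6 does not say whether its general rule or the table cell governs when they differ.

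**Working it through.** The plan states no figure on this point to reproduce. The check is to read off the dose each cell names.

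**Inputs.** Table 6, Cohort 2 column: 7 two-step rows (4, then 2.4 mg QW) and 3 three-step rows (6 mg 2-on/1-off, then 4, then 2.4 mg QW); 7 + 3 = 10. Section 6.6: one level down. The Cohort 1 column of Table 6 shows that one level below 4 mg QW is 2.4 mg QW.

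**Case 1: on 4 mg QW after one episode.** Only a two-step row gives 4 mg QW at a first episode. Suppose it was Grade 4 neutropenia. Nine rows remain (6 two-step, 3 three-step), and the patient has a first event in one of them.

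| Row of the new event | Counted per row (episode 1) | Counted across toxicities (episode 2) |
|---|---|---|
| 6 other two-step rows | 4 mg QW | 2.4 mg QW |
| Grade 2 diarrhea, Grade 3 diarrhea, other Grade 3 nonhematologic | 6 mg 2-on/1-off | 4 mg QW |

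Rows naming a lower dose: 0 of 9 per row, 6 of 9 across toxicities. The three three-step rows name no lower dose on either count.

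**Case 2: on 4 mg QW after two episodes**, for example two episodes of Grade 2 diarrhea, followed by a first event in a different row.

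| Row of the new event | Counted per row (episode 1) | Counted across toxicities (episode 3) |
|---|---|---|
| Other three-step rows | 6 mg 2-on/1-off | 2.4 mg QW |
| Two-step rows | 4 mg QW | no third step listed |

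Here the across-toxicity count does reach 2.4 mg QW in the three-step rows, so the absence of a lower dose holds only on the per-row count.

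**Dose sizes.** Mean weekly dose of 6 mg 2-on/1-off: 6 × 2 / 3 = 4.0 mg, the same as 4 mg QW. Dose per infusion against 4 mg: 6/4 − 1 = +50%. One level down: 2.4/4 − 1 = −40%.

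**Against Section 6.6 in Case 1.** Grade 3 diarrhea and other Grade 3 nonhematologic events fall under the one-level rule, which gives 2.4 mg QW; the cells give 6 mg 2-on/1-off or 4 mg QW. Grade 2 diarrhea is outside that rule, so its row has the gap but not the conflict.

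**Against the apparent intent.** The current amendment's rationale presents 2-on/1-off as something to try before dose reduction. SAP Section 7.8.1 counts planned reductions only from 6 to 4 mg and from 4 to 2.4 mg. Table 10 moves a patient on 4 mg QW to 2.4 mg QW. All three point to a downward ladder that starts from the current dose.

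**The case against.** The strongest reply is that a site would not follow these cells literally, because other text stands in the way.

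- All three rows first require a hold until the event is Grade 1 or lower, so nobody is dosed through the toxicity.
- Re-escalation needs Medical Monitor approval, so a cell naming 6 mg does not by itself authorise a move up from 4 mg. A reader might infer that Table 6 orders a dose increase; read together with Section 6.6, it does not.
- Section 6.6.2 says that a lower dose or frequency should be considered for diarrhea of Grade 2 or higher, depending on its severity and course. Two of the three rows are diarrhea rows.
- The table header directs questions to the Medical Monitor, Section 4.5 requires approval to restart after serious related reactions, and interruptions have 14-day (diarrhea) and 28-day limits.
- The Cohort 1 column, headed 4 mg QW, gives 2.4 mg QW in all ten corresponding rows, and a sensible site could borrow it.

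These points stand as limits on harm. The approval rule can stop a move up but does not tell anyone to go down. Section 6.6.2 asks for consideration, not a named dose, and does not cover the nonhematologic row. The header helps only a site that sees a question, whereas the cell reads as a complete instruction. Nothing tells sites to cross into the Cohort 1 column.

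It can also be said that the three-step rows depart from the one-level rule on purpose, and that specific text governs over general. The departure is deliberate for a patient on 6 mg QW, where the amendment explains it. That explanation does not extend to a patient already reduced. If the cell does govern, the result is simply no reduction.

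**Conclusion.** The point holds within stated limits. For a Cohort 2 patient on 4 mg QW after one earlier two-step episode, three rows name no lower dose for a new toxicity on either count. For two of them this conflicts with Section 6.6. A reader might infer that the same is true of every patient on 4 mg QW. It is not: after two earlier episodes, counting across toxicities gives 2.4 mg QW in those rows, and only the per-row count leaves the gap.

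The difference at stake is 2.4 mg QW against a mean of 4.0 mg per week, given either as 4 mg QW or as 6 mg infusions. The row counts describe table entries, not patients. The documents give no rate of second toxicities, so the frequency of such sequences is unknown. A reader might also look for an effect on the trial's inference; there is none on ORR, power or error rates. This is a patient-safety wording fault that is worth correcting because correction is cheap. The conclusion assumes that the two counts are the plausible readings of an undefined term and that one level below 4 mg QW is 2.4 mg QW.

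**What to change.** In Section 6.6 and Table 6, use the form Table 10 already uses and state that:

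1. steps count from the patient's current dose and regimen;
2. a reduction made for one toxicity carries over to all others, so a patient on 4 mg QW goes to 2.4 mg QW;
3. 6 mg two weeks on, one week off applies only to patients still on 6 mg QW;
4. no row raises the dose without the approval Section 6.6 requires.

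Define an episode, and tidy the GI-bleeding cell, which reads "Decrease to 4 mg QW for first episode and to 2.4 mg QW for second episode 1 dose level" and ends in leftover words. It would also help to name the action for a further dose-reducing event at 2.4 mg QW. The choice of dose levels stays with the sponsor.

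The cost is a wording change by amendment or clarification letter, with no added patients, visits or procedures.

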## **6.6 DOSE MODIFICATION AND TOXICITY MANAGEMENT GUIDELINES**

Dose modification associated with AL101 is described below in [Table 6](#).

The causality assessment system proposed by the World Health Organization Collaborating Centre for International Drug Monitoring, the Uppsala Monitoring Center (WHO-UMC) will be used by the Investigator for assessing drug-related (certain, probable/likely, possible) non-hematological Grade 3 (except isolated Grade 3 electrolyte abnormality that are not associated with clinical signs or symptoms and are reversed with appropriate medical intervention within 48 hours) and hematological Grade 4 toxicities will lead to a 1 dose level reduction for AL101. For easily manageable Grade 1 or 2 toxicity, no dose reductions are required, but careful observation and treatment is required. Dose modification of intolerable Grade 2 toxicity will be evaluated on a case-by-case basis with the Sponsor. Re-escalation of the dose following a dose reduction is allowed only after discussion and approval of the Sponsor's Medical Monitor. Maximum AL101 treatment interruption allowed is 28 days; treatment interruption longer than 28 days will result in discontinuation of patient from the study. Additional treatment guidelines may be implemented by the Investigators, with agreement of the Sponsor/Medical Monitor, as needed to ensure patient safety.

 "The use of the WHO-UMC system for standardized case causality assessment" a communication by WHO-UMC in 2011; [https://www.who-umc.org/media/164200/who-umc-causality-assessment\\_new-logo.pdf](https://www.who-umc.org/media/164200/who-umc-causality-assessment_new-logo.pdf)

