Dose Modification Criteria for AL101 -Related Adverse Events	AL101 modification	
	Note: for any questions, please contact the Sponsor's Medical Monitor.	
	Cohort 1 (4 mg QW IV)	Cohort 2 (6 mg QW IV)
	
If colitis is suspected please refer to Section 8.4.2, Table 10 for management guidelines for colitis.
 
If treatment interruption is longer than 28 days, the patient will be discontinued from the study.
	
If colitis is suspected please refer to Section 8.4.2, Table 10 for management guidelines for colitis.
 
If treatment interruption is longer than 28 days, the patient will be discontinued from the study.

Grade 3 or 4 gastric hemorrhage	
Permanently discontinue AL101 (refer to Section 4.5 for early withdrawal of patients from therapy or assessment).
	
Permanently discontinue AL101 (refer to Section 4.5 for early withdrawal of patients from therapy or assessment).

QTcF > 500 msec confirmed by at least one repeat ECG and at least 50 msec above baseline	
Interrupt if needed to optimize electrolyte management. If persists after electrolyte optimization (including dose modification of AL101 if necessary), discontinue.
 
If treatment interruption is longer than 28 days, the patient will be discontinued from the study.
	
Interrupt if needed to optimize electrolyte management. If persists after electrolyte optimization (including dose modification of AL101 if necessary), discontinue.
 
If treatment interruption is longer than 28 days, the patient will be discontinued from the study.

AST or ALT > 5 times the institutional ULN	
Interrupt AL101 until resolution to <math>\leq</math> Grade 1 and then resume at 1 dose level lower (i.e., 2.4 mg QW). Refer to Section 8.4.1 for hepatic function abnormalities and Section 8.4.5 for drug-induced liver toxicity management.
 
If treatment interruption is longer than 28 days, the patient will be discontinued from the study.
	
Interrupt AL101 until resolution to <math>\leq</math> Grade 1 and then decrease dose to 4 mg QW for first episode and to 2.4 mg QW for second episode.
 
Refer to Section 8.4.1 for hepatic function abnormalities and Section 8.4.5 for drug-induced liver toxicity management.
 
If treatment interruption is longer than 28 days, the patient will be discontinued from the study.

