### 8.4 ADVERSE EVENTS OF SPECIAL INTEREST

An adverse event of special interest (AESI) is one of scientific and medical interest specific to understanding of the Investigational Product and may require close monitoring and rapid communication by the investigator to the Sponsor. An AESI may be serious or non-serious. The rapid reporting of AESIs allows ongoing surveillance of these events in order to characterize and understand them in association with the use of this investigational product. AESI for AL101 include events that are mediated by disruption of the Notch signaling pathway and can be attributed to the drug's mechanism of action with no clear alternate etiology and which may require more frequent monitoring and/or interventions. All AESI must be reported in the AESI section of the CRFs.

AESI observed with AL101 are detailed in the sections below and include hepatic function abnormalities, colitis, infusion reactions (including anaphylaxis), keratoacanthoma, and potential drug-induced liver injury (DILI). For dose modifications and toxicity management for the AESI, please refer to Section 6.6.

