Grade 3-4	Permanently discontinue investigational product	
 
Promptly initiate empiric IV methylprednisolone 2 to 4 mg/kg/day or equivalent
 
Monitor stool frequency and volume and maintain hydration
 
Urgent GI consult and imaging and/or colonoscopy as appropriate
 
 
Caution: Ensure GI consult to rule out bowel perforation
 
Once improving, gradually taper steroids over <math>\geq</math>28 days and consider prophylactic antibiotics, antifungals and anti PCP treatment (please refer to current NCCN guidelines for treatment of cancer-related infections [Category 2B recommendation])

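### For Grade 3 colitis without GI bleeding or a hemoglobin drop, Table 10 stops AL101 permanently, while Table 6, to which Section 8.4 sends AESI dosing, literally allows it to be resumed

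*Protocol*

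**What the plan says.** Section 8.4.2 sends the management of colitis to Table 10, whose Grade 3-4 row reads "Permanently discontinue investigational product". The parent Section 8.4 lists colitis among the AESIs and adds: "For dose modifications and toxicity management for the AESI, please refer to Section 6.6".

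Section 6.6 opens with a general rule. Drug-related events that are "non-hematological Grade 3 (except isolated Grade 3 electrolyte abnormality that are not associated with clinical signs or symptoms" (and reversed within 48 hours), together with "hematological Grade 4 toxicities will lead to a 1 dose level reduction for AL101". Table 6 then gives event-specific rules. It has no row for colitis. Its residual row covers "Any other AL101-related Grade 3 nonhematologic adverse event except electrolyte abnormalities that may be managed with supplements". The action is to hold drug until the event is Grade 1 or better, then restart at 2.4 mg weekly in Cohort 1. For Cohort 2 the text is "then change dose regimen to 6 mg 2 weeks on / 1 week off for the first episode", stepping down to 4 mg and 2.4 mg weekly for later episodes. A hold of more than 28 days ends treatment.

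Table 6 mentions colitis twice. The row for GI bleeding or an unexplained hemoglobin drop contains a sentence beginning "If colitis is suspected please refer to Section", which leads to Section 8.4.2 and Table 10. The Grade 4 diarrhea row advises a GI consult to look for colitis. The Grade 3 diarrhea row says nothing about it.

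**The concern.** An investigator with a patient who has related Grade 3 colitis can follow the protocol's own references to two incompatible instructions. Table 10 ends treatment. The route from Section 8.4 to Section 6.6 reaches a row that brings the patient back on drug.

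The direction of the possible error matters. Section 8.4.2 regards intestinal inflammation as probably on-target and reports Grade 3 colonic ulceration/Grade 3 diarrhea as dose-limiting in the earlier solid-tumor study. In Cohort 2 the residual row restarts at 6 mg per infusion. Section 1.4.1 records dose-limiting toxicities at 6 mg and 8.4 mg in that study, and 4 mg as the weekly maximum tolerated dose recommended by the previous developer.

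A related gap lies in the Grade 3 diarrhea row. Section 8.4.2 counts severe diarrhea among the signs of potential colitis, but the row that decides whether to resume after Grade 3 diarrhea has no pointer to Table 10.

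**Working it through.** The plan states no figure to reproduce. The check sets the two dosing rules side by side, case by case, for events judged related to AL101.

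| Case | Table 10 | Section 6.6 / Table 6 | Agree? |
|---|---|---|---|
| Grade 4 colitis | Stop permanently | Grade 4 non-hematologic row: stop permanently | Yes |
| Grade 3, with GI bleeding or hemoglobin drop | Stop permanently | GI-bleeding row refers suspected colitis to Table 10 | Yes, through the pointer |
| Grade 3, neither, Cohort 1 | Stop permanently | Residual row: hold, then 2.4 mg weekly | No |
| Grade 3, neither, Cohort 2 | Stop permanently | Residual row: hold, then 6 mg two weeks on, one off | No |

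1. *Does the residual row cover Grade 3 colitis?* It takes in any related Grade 3 nonhematologic event not dealt with elsewhere in the table. Colitis has no row, and the only exemption is for electrolytes. On its face, colitis is covered.

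2. *Does any text take it out again?* The one pointer from Table 6 to Table 10 sits in the bleeding/hemoglobin row, which the remaining cases do not enter. No sentence gives Table 10 precedence.

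3. *How far apart are the rules?* Table 10 gives no further drug. In Cohort 2 the residual row gives 2 × 6 mg = 12 mg every 3 weeks, an average of 12/3 = 4 mg per week. In Cohort 1 it gives 2.4 mg per week. The rules diverge in outcome only if the event settles to Grade 1 or better within 28 days; otherwise Table 6 also ends treatment.

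4. *What happens at Grade 3 diarrhea?* Table 8 labels Grade 3 as severe, so this grade matches the sign named in Section 8.4.2. The row resumes AL101 after resolution with no reference to colitis. Among the diarrhea rows only Grade 4 raises colitis, and there the drug is stopped in any case.

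**The case against.** The best defense is that a specific rule displaces a residual one. Colitis has its own table with its own dose-modification column, Section 8.4.2 points directly to it, and the Amendment 3 summary mentions the two-on, one-off schedule for Grade 2 colitis but not Grade 3. This stands as evidence of intent: Table 10 is very probably meant to govern. It does not settle the text, because Section 8.4 itself directs AESI dosing to Section 6.6.

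Safeguards also exist. Section 4.5 requires dosing to be interrupted for a related serious reaction, with restart on Medical Monitor approval. Table 7 requires related AESIs to be reported within 24 hours. Table 6 invites questions to the Medical Monitor. These reduce the risk, but they depend on the event being serious, recognized as an AESI, or queried.

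Several stronger readings are tempting and are not supported:

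- *The general Grade 3 sentence in Section 6.6 is a second, independent contradiction.* It is a default that Table 6 departs from repeatedly: Grade 3 gastric hemorrhage is stopped, Cohort 2 Grade 3 diarrhea gets a schedule change first, and Grade 4 febrile neutropenia is stopped. Its silence on colitis shows nothing particular to colitis.
- *Colitis is the odd one out among AESIs in lacking a row.* Keratoacanthoma has none either. The row "AST or ALT > 5 times the institutional ULN" is not the hepatic AESI as Section 8.4.1 defines it, which is ALT or AST above 3 times ULN with bilirubin above 2 times ULN.
- *Diarrhea is never checked for colitis.* Section 8.4.2 calls for a work-up when signs of colitis appear, and Section 6.6.2 covers considering infectious causes and managing diarrhea with signs of colitis. What is missing is a cross-reference. Nor does the text make Grade 3 diarrhea colitis in itself, or support a pointer at Grade 2, since Section 8.4.2 speaks of severe diarrhea.

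**Conclusion.** The conflict is real but narrow. For related Grade 3 colitis without GI bleeding or a hemoglobin drop, the protocol as written gives both permanent discontinuation and interruption followed by resumption, and does not say which prevails. The missing pointer in the Grade 3 diarrhea row is a smaller gap of the same kind.

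The issue is minor. It is a patient-safety wording error with a probable intended answer and partial safeguards. It leaves ORR, the sample size and the efficacy analysis untouched. No count of affected patients is offered, because the documents available give no colitis rate. The conclusion rests on reading the residual row literally, and on the absence of any precedence statement in the protocol text available. Instructions in manuals or site communications were not available.

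**What to change.** Make three wording changes in Section 6.6:

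1. Add a line to Table 6: *Colitis: see Section 8.4.2, Table 10, which governs.* Exclude colitis from the residual Grade 3 row.
2. In the general Grade 3 sentence that opens Section 6.6, add *except as specified in Table 6 or Table 10*.
3. Copy the GI-bleeding row's existing sentence, beginning "If colitis is suspected please refer to Section", into the Grade 3 diarrhea row for both cohorts, so that suspected colitis is assessed before AL101 is resumed.

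The diagnosis of colitis should stay with the investigator under the existing text of Sections 8.4.2 and 6.6.2 and Table 10. The cost is a short amendment or site clarification, with no new visits, assessments or stopping criteria. The downside is that a few more patients may be evaluated for colitis and stopped permanently under Table 10.
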